6.3 FEASIBILITY ASSESSMENT

drafted a previous version of this protocol which has been reviewed by the EMA CHMP. The previous protocol included a feasibility component to guide the final design of the study. An study team including researchers in epidemiology, survey research, instrument development, and biostatistics conducted a feasibility evaluation study in 30 infusion centres located in the 5 European countries of interest to assess the centres' interest in participating in this study, clarify local requirements for study approval, and refine the protocol regarding sample size expectations and study procedures The selection of participating centres for the feasibility component was not intended to be representative in each country but merely to guide the design of this study.

The specific goals of the feasibility evaluation were as follows:

- To assess the interest of infusion centres in participating in a research study.
- To obtain estimates of the number of patients treated with MabThera.
- To assess whether the centres meet requirements for both patient enrolment and patient medical record abstraction.
- To evaluate the characteristics of infusion centres.
- To obtain input from the infusion centres about patient flow, centre processes, feasibility of the study procedures, and how to minimise impact on day-to-day activities.
- To assess whether infusion centre records provide the patient disease information needed for the medical record abstraction.
- To ascertain the current counselling practices of health care providers (HCPs) at the centre to evaluate whether the patient questionnaire can be completed prior to the provision of any new counselling regarding the MabThera PAC content.
- To collect information about EC requirements for the medical record abstraction and patient survey.
- To evaluate the optimal time window for medical record abstraction, the target number of patients per centre to be recruited into the survey, and survey enrolment periods.

The feasibility component also evaluated the potential for using existing registries of biological agents in the 5 European countries to capture off-label use of MabThera. The goal was to evaluate registries of biological therapies as a source of supportive data in

addition to the drug utilisation study (DUS). Registry data could complement the study design included in the current draft of the infusion centre study protocol, assuming that the registries capture MabThera use for both RA and other autoimmune diseases, their data can be accessed for research purposes, and they collect a minimum set of variables necessary to classify use as on- or off-label. This revised version of the protocol removes the supplementary analysis of off-label use using those registries. This change has been implemented because the marketing authorisation holder has submitted assessments of rituximab off-label usage in autoimmune indications from a health care claims database and cumulative post-authorisation exposure in the EU MabThera Risk Management Plan version 13 (Section SV.4, submitted in October 2014) and periodic benefit-risk evaluation reports (PBRER) 1058003 (submitted January 2015 covering the period from 18 November 2012 to 17 November 2014, Sections 5.2.1.2, 5.2.1.3, 5.2.2.3, 5.2.3.1). Should further information be required, the marketing authorisation holder may conduct additional investigations using biologic registries and submit these in future PBRERs.

The feasibility evaluation (was submitted to EMA, as was the final version (V1) of this protocol, which incorporates the results of the feasibility evaluation and its recommendations. The outcome of the EMA review of V1 final was described in EMA/411582/2014.

6.4 STUDY RATIONALE

Administration of MabThera takes place in special settings, primarily infusion centres. For study purposes, we define an infusion centre as a location—doctor's office, clinic, hospital, one or more sites within a health care building—where infusions of MabThera might take place. The above FUMs require close coordination of activities to avoid duplication of effort and minimise the administrative burden on participating infusion centres. Therefore, this protocol plans for a single study to address both FUMs, with the exception of the UAT, which has previously been evaluated and shown to be acceptable.

The study will be conducted in infusion centres to (1) characterise the indications for which MabThera is being used and (2) evaluate the use of the PAC in patients receiving the medication for non-oncology conditions at infusion centres.

The feasibility assessment conducted by identified some variability in the distribution of the PAC across centres in the 5 European countries and indicated that some centres are providing educational information on safe use of MabThera other than the PAC. The small number of centres (N = 30) participating in the feasibility study was not selected to be representative of all treatment facilities in each country. Therefore, this study will determine via the patient questionnaire whether additional information is provided to the patient. Additional input regarding these materials can arise in communications with study sites during the course of the study.

7. RESEARCH QUESTION AND OBJECTIVES

7.1 OBJECTIVES

- Specific aim 1: To quantify and characterise off-label use through an evaluation of the disease and characteristics of patients treated with MabThera for non-oncology conditions.
- Specific aim 2: To evaluate the extent to which patients receive and read the PAC, knowledge of the PAC content among patients receiving MabThera for nononcology conditions at infusion centres, and whether distribution of the PAC may influence patient actions.

8. RESEARCH METHODS

8.1 STUDY DESIGN

8.1.1 Overview of Study Design

This DUS is a multinational, multicentre study involving the retrospective chart review of MabThera users' medical records in non-oncology indications (Figure 1). Nested in the study, a cross-sectional survey of patients receiving MabThera will be performed starting from the date of the first medical record data abstraction (Figure 1).

A geographically dispersed and diverse set of infusion centres in the United Kingdom (UK), Germany, France, Italy, and Spain will be recruited to participate in the study. At each participating centre, de-identified data will be retrospectively abstracted from medical records on treatment indication (RA, SLE/LN, other) and selected patient and disease characteristics for all patients receiving MabThera for a non-oncology condition, during a 10-month data collection period. The survey will also be conducted during the same 10-month period, and will prospectively collect information on patient characteristics, and will include questions about patient knowledge on the risk of infections including PML, patient receipt and review of the PAC, and any actions the patient has taken as a result of receiving the PAC.

Final approved protocol Q2 2015 Q4 2015 Q3 2016 Q1 2017 Start-up Phase Questionnaire Pilot validation Analysis ICF + Data collection (medical abstraction and Country regulatory submissions and parallel survey administration Reporting Site sampling & selection (up to 10 months) (6 months) Site Contracting EDC setup Study period Inception cohort of all patients treated with Mabthera in NO prior the index date Index date (country & site Last patient data Final report to specific): PRAC (March 27 abstracted Start of the first Medical record 2017) & Data lock data abstraction

Figure 1: DUS and PAC Survey Overview

ICF: Informed Consent Form; NO: non-oncology conditions; PRAC: Pharmacovigilance Risk Assessment Committee; Q: quarter.

Drug Utilisation Study

The index date (start date of medical record abstraction for the first patient) for the study will be selected for each country and correspond to the date when a site becomes aware of the study objectives. After all approvals from national EC and regulatory authorities have been granted, all medical record data will be retrospectively reviewed until the index date; this approach will ensure the data collected are fully reflective of real world administration of MabThera and not influenced by study awareness. The retrospective review of medical records will occur within a 12-month "look-back" period prior the selected index date (i.e., the eligibility period). The observation period for consenting patients corresponds to the interval between the first and last infusion dates of MabThera, if treatment is discontinued before the index date. If the patient is still on MabThera at the index date, then the observation period is the interval between the first infusion date and index date. Furthermore, if a patient stops and re-starts MabThera during the observation period, all repeated treatment intervals will be captured.

Patient Alert Card survey

The PAC survey will be conducted after the index data and concomitantly with the medical record abstraction process. The PAC survey will be completed once by each patient after informed consent has been provided.

Duration of the study

The planned duration of the study (i.e., both medical record and survey data collection) is approximately 16 months after the recruitment of the first patient. This period takes into account 10 months of data collection and a 6 month period between last patient recruited and final study report.

will closely monitor inclusion rates. If projected recruitment rates indicate that patient targets may not be achieved in the planned recruitment period, consideration will be given to extending the recruitment period, initiating additional sites within the 5 existing countries, and/or expanding the study into additional EU countries.

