Study coordinators at infusion centres will be responsible for identifying and recruiting patients as they are scheduled or come to the site for their MabThera infusion. For the patient survey, patients meeting the eligibility criteria who visit the participating infusion centres during the data collection period will be given the opportunity to participate in the patient survey until the infusion centre recruitment goal is met. Sites will keep a simple log with information on the number of patients approached about the survey and reasons for refusal for those who refuse to participate. Sites will also keep a log of all eligible patients from whom consent is requested whether they participate or not to the study, and reason for refusal for those who refuse to give consent. The logs will also include minimal information such as age, sex, and clinical indication for MabThera depending on country data privacy policies. The logs will not include any patient identifier and will be kept separate for the survey and medical record abstraction components.

Infusion Centre Recruitment

Approval from each relevant IRB/independent EC will be obtained prior to study start in each country and documented in a letter to the centre specifying the date on which the IRB/EC met and granted approval. Centres will be contacted to confirm their eligibility, assess their interest in participating in the study, and assess the feasibility of implementing data collection.

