A "data not available" response will be available where appropriate for those record abstraction items for which data may be missing from patient records. This type of response will help reduce missing data and will document the overall gaps in record keeping.

A brief pilot test of the translated version of the abstraction form will be conducted in each country, and the abstraction form in one or more countries may be adjusted based on the results of this pilot.

A draft version of the medical record abstraction form is included with this document (Appendix 1).

Off-Label Use Definition

The definition of off-label use of MabThera will be based on the use for a non-oncology disease or medical condition other than RA and GPA/MPA covered by MabThera SPC.

In absence of labelled indications, potential off-label use could include, but is not limited to, the following conditions:

- Ankylosing spondylitis
- Psoriatic arthritis
- Undifferentiated spondyloarthritis
- Juvenile idiopathic arthritis
- SLE
- Systemic vasculitis

- Eosinophilic GPA
- Inflammatory myopathies
- Behçet disease
- Sjögren syndrome
- Nephrotic syndrome
- Glomerulonephritis
- Multiple sclerosis/neuromyelitis optica
- · Pemphigus vulgaris
- Polydermatomyositis
- · Mixed connective tissue disease

Patient Survey data

The patient questionnaire has been developed following standard survey methodological principles and will be cognitively tested with patients in each of the target countries. Modifications will be made to the questionnaire based on the results of testing, and some variations to the questionnaire are anticipated based on country-specific requirements.

The questionnaire will include an introductory section with questions to confirm eligibility. The majority of the questionnaire items will be closed ended, ensuring that the resulting data are easy to analyse and interpret. Closed-ended questions are generally more efficient than open-ended questions (or open-ended text fields) and more conducive to summarisation and statistical analyses.

The questionnaire will collect the following information (please refer to Appendix 1 for the draft questionnaire):

- Demographics (e.g., age, sex, ethnicity)
- Patient previous history of PML or other serious infectious diseases
- Whether the patient has received a previous treatment with MabThera, if so, number of prior infusions during the last 12 months
- Patient understanding or awareness of the following:

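### Section 8.1.1 gives the index date two meanings; under the one Figure 1 uses, the 12-month record look-back includes infusions given after the site knew of the study

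*Protocol*

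**What the plan says.** Under Drug Utilisation Study, Section 8.1.1 begins its definition with "The index date (start date of medical record abstraction for the first patient" and goes on to say that this date "will be selected for each country and correspond to the date when a site becomes aware of the study objectives". The date is the cut-off for the record component: "all medical record data will be retrospectively reviewed until the index date", within a 12-month look-back before it. The stated purpose is that the data are "fully reflective of real world administration of MabThera and not influenced by study awareness".

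Figure 1 labels the index date only as the start of the first medical record abstraction. It calls the date specific to country and site, whereas the text sets it by country.

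Other sections describe what happens at sites before abstraction:

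- Section 8.2 (Infusion Centre Recruitment): centres are contacted to confirm eligibility, "assess their interest in participating in the study, and assess the feasibility of implementing data collection".
- Section 8.3: "A brief pilot test of the translated version of the abstraction form will be conducted in each country".
- Figure 1: site selection, contracting and EDC set-up are start-up items.
- Section 8.7: site staff are trained on the forms before the study is fielded.
- Section 9.3: the protocol goes to the ethics committee through the CRO or the centre's own staff, and is approved before initiation.
- Section 9.2: signed consent is needed before a patient takes part in either component.

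**The concern.** A cut-off can be the day a site learns what the study is about or the day it opens the first chart. The protocol treats these as one date, but its own sequence of activities separates them. Only the first meaning delivers the property that Section 8.1.1 claims. The second, which is the one in Figure 1 and the one a site can most easily apply, lets in prescribing and record-keeping from after the site knew of the study.

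The result at stake is the main analysis of the drug utilisation component in Section 8.6, the proportion of off-label use. Section 8.9 discusses selection of sites and patients, and volunteer bias in the survey. It does not mention this route of bias, so a reader of the report would take the assurance in 8.1.1 at face value.

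**Working it through.** **Step 1. The definitions side by side.**

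| Place | Event that fixes the date | Level |
|---|---|---|
| 8.1.1, parenthesis | First patient's chart abstraction starts | Country |
| 8.1.1, same sentence | Site becomes aware of the objectives | Country, though awareness belongs to a site |
| Figure 1 | First record abstraction starts | Country and site |

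The level matters as well as the event. If one date is set per country, centres that join at different times learn of the study on different dates, and a single date cannot match them all.

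**Step 2. Can the two events fall together?** Section 8.1.1 allows record review only after ethics and regulatory approvals. Consent must be signed before a chart is abstracted (9.2), and the coordinator has to explain the study to obtain it (8.2). Training and contracting also come first. So at any site the abstraction start follows awareness. The order is fixed by the protocol; the length of the interval is not.

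**Step 3. How long is the gap?** The protocol states no awareness date, so this is a range under assumptions. Take the planned start of data collection, Q4 2015 (Section 5), as a site's abstraction start; a site opening later would have a longer gap for the same awareness date.

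- Shortest gap = 1 October 2015 minus the latest assumed awareness date
- Longest gap = 31 December 2015 minus the earliest assumed awareness date
- Months = days / 30.4375; share = unrounded months / 12

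| Assumed awareness | Shortest | Longest | Share of the 12 months |
|---|---|---|---|
| Q2 2015 (first quarter shown in Figure 1) | 93 days = 3.1 months | 274 days = 9.0 months | 25% to 75% |
| Q3 2015 (planned ethics approval, Section 5) | 1 day = 0.0 months | 183 days = 6.0 months | 0% to 50% |
| 8 September 2015 (version 3.0 date) | 23 days = 0.8 months | 114 days = 3.7 months | 6% to 31% |

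These are shares of calendar time, not of the off-label estimate.

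**Step 4. Who is exposed?** Section 8.3 defines off-label use by the disease treated. The abstraction form (Appendix 1, item 7) records the primary condition for which the drug was prescribed. A patient who started before the site was aware, and is still being infused, normally has a condition already on record. Mainly patients whose first infusion falls in the gap can be affected. The form collects the date of first infusion (item 5), and Section 8.6 plans separate estimates for incident and prevalent patients, so exposure could be examined.

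**The case against.** The strongest reply is that Section 8.1.1 already states the right rule: the date is chosen to match awareness, and charts are then reviewed, at whatever later time, back from that date. On that reading the only faults are the parenthesis and the label in Figure 1. It is a fair account of the intent. It still leaves sites with a sentence and a figure that point to abstraction start, so the wording has to change.

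Four further points limit the concern, and they stand:

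- **Length.** The text of Figure 1 does not date site contact within start-up, so the Q2 2015 row is weakly supported. On the version 3.0 date the gap may be under one month.
- **What sites knew.** A reader might infer that centres knew off-label use was under audit from the first call. The documents do not say so. A call about eligibility and interest need not disclose objectives, the form pilot is per country and not per site, and Section 8.3 has physicians told that the ultimate goal is to evaluate the use of the alert card. Staff can learn the off-label aim from the protocol, but when they do is not stated.
- **Direction.** A reader might infer that awareness lowers the off-label proportion. That is plausible, but nothing in the documents establishes it.
- **Remedy.** Closing the window at the first contact of any kind would misfire. The 30 feasibility centres (Section 6.3) were approached before version 1.0 of 27 July 2012, which used the feasibility results. For any of them taking part, the window would end in or before 2012, ahead of the March 2013 GPA/MPA approval (Section 6.2).

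**Conclusion.** The point holds as a contradiction in the definition and an assurance that the Figure 1 rule cannot deliver. With abstraction start as the cut-off, the look-back includes infusions given after the site knew of the study. This rests only on the protocol's own order of approval, contracting, training, consent and abstraction.

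The size is open. The gap runs from under one month to several months, depending on an awareness date that has to be assumed. It would be wrong to report that 25% to 75% of the off-label data are affected: that range takes the earliest anchor and counts calendar months, while the exposure lies mainly with patients newly started in the gap. Neither the direction nor the size of any shift in the off-label proportion can be derived. The wording should be corrected; the finding does not show that the estimate is biased.

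**What to change.** - In Section 8.1.1 and Figure 1, define the index date per site as the documented date on which the site was informed of the objectives of the current study, for example receipt of the current protocol. State that the earlier feasibility contact does not count.
- End the 12-month eligibility window on the day before that date.
- Introduce a separate abstraction start date for operations and for the opening of the survey, which Section 8.1.1 already ties to the first abstraction.
- In the abstraction form (Appendix 1), tie the items on the most recent infusion (items 6 and 11, RA9 to RA14) and on medication in the past 12 months (item 12) to the index date. Without this, the new cut-off would not be enforced in the data.
- As a check, flag centres that took part in the feasibility evaluation and repeat the off-label estimate without them.

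The cost is wording in one section and one figure, edits to the form, and one recorded date per site. Section 8.9 already requires site selection to be documented, so that date should be obtainable. The small downside is that the data window ends somewhat earlier.

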8.1.2 Number of Patients Observed in the Study

Based on the results of a feasibility evaluation, it is estimated that 1,000-1,500 medical records (200-300 per country) of patients receiving MabThera will be abstracted and 500-700 patients (approximately 100 per country) will complete the questionnaire at participating infusion centres.

8.1.3 Centres

This study will be conducted at approximately 10-15 centres in approximately 5 countries, in order to recruit the estimated number of patients for medical record abstraction and survey participation, as described in Section 8.1.2. Additional countries and centres may be added or substituted if underperforming.

8.2 POPULATION

Infusion centres that are representative of the non-oncology use of MabThera in the UK, Germany, France, Italy, and Spain will be recruited to participate in the study. Each centre will be expected to retrospectively abstract data from medical records for non-oncology MabThera patients and to enrol an appropriate number of patients who will complete the patient questionnaire component of the study; the target is a total of 100 survey participants per country. The survey participants will be recruited during a 10-month period concomitantly with the medical record abstraction process.

Infusion Centre Eligibility

To participate in the study (DUS and PAC survey), each infusion centre must meet all of the following criteria:

- 1. Administer MabThera to a least 20 patients who would meet the eligibility criteria in the past 12 months; and
- 2. Be able to provide a semi-private space for patient recruitment, the consent process, and completion of the patient questionnaire; and
- Have a staff member available to coordinate study activities.

Patient Eligibility for the study

Patients must meet the following inclusion criteria for study entry:

- 1. Patient is in the centre to receive an infusion for MabThera for a non-oncology indication during the study period
- 2. Patient is aged 18 years or older
- Patient provides informed consent for medical record abstraction and/or survey participation
- 4. Patient participating in the survey can read and understand English, Spanish, Italian, French, or German, according to the country.

No Exclusion criteria will apply for medical record abstraction participation although patients who meet any of the following criteria will be excluded from the survey participation:

- 1. Patient has previously already completed the MabThera survey
- 2. Patient has participated in the past 12 months in a clinical trial in which MabThera was one of the treatments being evaluated.

Study coordinators at infusion centres will be responsible for identifying and recruiting patients as they are scheduled or come to the site for their MabThera infusion. For the patient survey, patients meeting the eligibility criteria who visit the participating infusion centres during the data collection period will be given the opportunity to participate in the patient survey until the infusion centre recruitment goal is met. Sites will keep a simple log with information on the number of patients approached about the survey and reasons for refusal for those who refuse to participate. Sites will also keep a log of all eligible patients from whom consent is requested whether they participate or not to the study, and reason for refusal for those who refuse to give consent. The logs will also include minimal information such as age, sex, and clinical indication for MabThera depending on country data privacy policies. The logs will not include any patient identifier and will be kept separate for the survey and medical record abstraction components.

Infusion Centre Recruitment

Approval from each relevant IRB/independent EC will be obtained prior to study start in each country and documented in a letter to the centre specifying the date on which the IRB/EC met and granted approval. Centres will be contacted to confirm their eligibility, assess their interest in participating in the study, and assess the feasibility of implementing data collection.

Approximately 10-15 infusion centres in each country will be recruited to participate in this study. As part of the feasibility evaluation, Roche provided lists of infusion centres for potential participation. If the target number of participating infusion centres is not achieved, national study coordinators may be required to update and supplement the site lists. The final infusion centres recruited are not intended to reflect a random sample of all infusion centres for biologic treatments in the target countries but rather a generally representative sample of centres administering MabThera. Several factors will be evaluated to ensure a diverse representation of sites, including geographic location, infusion centre type (e.g., outpatient clinic or hospital-based infusion centre), medical specialty of physicians treating the patients (e.g., rheumatology vs. internal medicine), research experience (e.g., academic centre vs. community health centre), and casuistic purpose (e.g., centres that treat mainly off-labels patients vs. centres that treat mainly patients with RA). In addition, during site recruitment, data on site characteristics that may influence patients and their knowledge of the PAC will be collected (e.g., whether or not the PAC is being distributed at the infusion centre and counselling practices at the centre).

Following study start, information will be collected about the distribution or not of the MabThera PAC within each centre. For those infusion centres that are unable to participate or are not interested in participating, reasons for their refusal to participate in the study will be documented as part of the recruitment process.

Patient Selection and Recruitment

As patients come in for their MabThera infusions or shortly before the visit, the study coordinator at each site will confirm whether selected patients meet eligibility criteria for the study as specified in the study protocol. According to the eligibility criteria, a patient may be invited to participate in either the medical record abstraction component of the study, or both the medical record abstraction and survey components of the study; patients eligible for the latter may choose to participate in either or both components of the study. The study coordinator will present eligible patients with information about the study using a patient recruitment card and instructions. The study coordinator will invite interested and eligible patients to participate in the study, describe the nature of their participation, and obtain informed consent from patients willing to participate.

It is estimated that 20-30 patients will participate to the medical record abstraction in order to yield between 1000-1500 medical records in the DUS. For the patient survey, it is estimated that each infusion centre will recruit 10-14 patients, with the goal of 500-700 patients (approximately 100 patients per country) completing the survey. The estimates are based upon the anticipated number of eligible patients for participation identified in the feasibility evaluation and an adequate level of precision for the estimates (see Section 8.6). This final number of study participants depends on the actual number of patients filling a prescription within the established time frame and on actual response rates for the study.

For centres with a large volume of patients that will most likely reach the maximum number of patients, a patient sampling methodology will be considered to select the specific patients that will participate in the study. The sampling methodology will be designed with the goal of maximising the probability that each patient treated with MabThera will have an equal opportunity to be selected. In some sites, it is likely that all treated patients will be selected. The sampling approach for those sites with larger numbers of patients will be customised for the site (based on patient volume) and will be devised to achieve an efficient method of obtaining a representative patient sample in centres with varying patient administration systems. The sites will be asked to recruit patients for the study when the patients are at the physician practice for a scheduled visit.

Patient Alert Card Distribution

The PAC will be distributed to all patients receiving MabThera for non-oncology indications, as stated on the card.

